7.12.3 Vital Signs

In subjects who are not undergoing CSF collection (Cohorts 2, 4 to 8, and 10 to 18), vital signs will include body temperature (oral), respiratory rate, and orthostatic blood pressure and pulse (bpm). For orthostatic blood pressure, a drop in systolic blood pressure of ≥ 20 mm Hg, or in diastolic blood pressure of ≥ 10 mm Hg, or experiencing lightheadedness or dizziness is considered abnormal.

In subjects who have completed enrollment for Cohort 1 at the time of the protocol amendment 03 and in subjects who are undergoing CSF collection (Cohorts 3 and 9), vital signs include body temperature (oral), respiratory rate, supine blood pressure (resting more than 5 minutes), and pulse (bpm).

For SRD Cohorts 1 to 6 and 18 to 22, vital signs (oral temperature, respiration, pulse, and blood pressure) will be obtained at Screening, at Check-in (Day -1), on Days 1 through 5 (Final Visit)/ ET and at the Follow-up Visit. In Cohort 3, vital signs will be collected at approximately 5 hours postdose. In addition, orthostatic blood pressure will be measured in all cohorts except Cohort 3, at predose and at 2, 4, 6, 8, and 12 hours postdose in the first 24 hours after the initial dose of TAK-071 and then daily afterwards while subjects are confined in the phase 1 unit.

For MRD healthy volunteer Cohorts 7 and 8, vital signs (oral temperature, respiration, pulse, and blood pressure) will be obtained at Screening, at Check-in (Day -1), on Days 1 through 23 (Final Visit)/ ET and at the Follow-up Visit. In addition, orthostatic blood pressure will be measured at predose and at 2, 4, 6, 8, and 12 hours postdose in the first 24 hours after the initial dose of TAK-071 and then daily afterwards while subjects are confined in the phase 1 unit.

For MRD healthy volunteer Cohort 9, vital signs (oral temperature, respiration, pulse, and blood pressure) will be obtained at Screening, at Check-in (Day -1), on Days 1 through 30 (Final Visit)/ ET and at the Follow-up Visit.

For MRD + Donepezil pretreatment healthy volunteer Cohorts 10 to 12, vital signs (oral temperature, respiration, pulse, and blood pressure) will be obtained at Screening, at Check-in (Day -22), on Days -21 through -19, Days -10 through -1, Days 1 through 23 (Final Visit)/ ET and at the Follow-up Visit. In addition, orthostatic blood pressure will be measured at predose

and at 2, 4, 6, 8, and 12 hours postdose in the first 24 hours after the initial dose of TAK-071 and then daily afterwards while subjects are confined in the phase 1 unit.

For MRD Japanese healthy volunteer Cohorts 13 to 15, vital signs (oral temperature, respiration, pulse, and blood pressure) will be obtained at Screening, at Check-in (Day -1), on Days 1 through 30 (Final Visit)/ ET and at the Follow-up Visit. In addition, orthostatic blood pressure will be measured at predose and at 2, 4, 6, 8, and 12 hours postdose in the first 24 hours after the initial dose of TAK-071 and then daily afterwards while subjects are confined in the phase 1 unit.

For Cohort 16 in subjects with MCI or Mild AD, vital signs (oral temperature, respiration, pulse, and blood pressure) will be obtained at Screening, at Run-in Period (Day -49 and Day -21), at Check-in (Day -1), on Days 1, 2, 11, 20, 21, 22, 41, 42, 43, 52, 61, 62, and 63 (Final Visit)/ ET and at the Follow-up Visit. In addition, orthostatic blood pressure will be measured at predose and at 2, 4, 6, 8, and 12 hours postdose in the first 24 hours after the initial dose of TAK-071 and then afterwards on Days 2, 11, 20 to 22, 40 to 42, 51, and 60 to 62 (upon morning rising)/ ET.

For BA/FE Cohort 17, vital signs (oral temperature, respiration, pulse, and blood pressure) will be obtained at Screening and in each period at Check-in (Day -1), Day 1 (predose [within 45 minutes prior to dosing], and at 1, 3, and 12 hours postdose), and Days 2 through 5 (upon rising), Day 8 PK visit, Study Exit ([Day 8 of Period 3]/ ET and Follow-up Visit (Day 12 [±2]) of Period 3, as appropriate.

Descriptive statistics (N, mean, median, SD, minimum and maximum) of these vital signs will be summarized by the pooled placebo group, each TAK-071 dose level, TAK-071 overall, and overall total within each part (SRD cohorts, MRD cohorts, Cohort 16, and Cohort 17) for baseline, each postdose time point, and change from period baseline to postdose time points. Only the vital signs collected at the scheduled visits or time points will be included in the summary. No statistical tests will be performed for the observed vital signs.

All individual vital signs that meet Takeda's predefined criteria for markedly abnormal values ([Appendix B](#)) will be listed. The number and percentage of subjects with at least one postdose markedly abnormal vital sign measurement will be summarized. The mapping of the subjects who meet the MAV criteria for postdose vital sign parameters will be listed as a table. All postdose vital signs, including both scheduled and unscheduled measurements, will be included in the MAV summaries.

7.12.4 12-Lead ECGs

For SRD Cohorts 1 to 6 and 18 to 22, a standard 12-lead ECG will be recorded at Screening, Check-in (Day -1), Day 1 (predose [within 60 minutes prior to dosing], and at 0.5, 1, 2, 4, and 8 hours postdose), Days 2 through 5 (upon morning rising)/ ET and at the Follow-up Visit. Single ECGs will be taken at all visits. Continuous 12-lead Holter ECG monitoring will be conducted from 2 hours predose until 48 hours postdose in Cohorts 2, 4, 6, 18, and 19 only.

For MRD healthy volunteer Cohorts 7 and 8, a standard 12-lead ECG will be recorded at Screening, Check-in (Day -1), Day 1 (TAK-071 predose [within 60 minutes prior to dosing] and

at 0.5, 1, 2, 4, and 8 hours postdose), Days 2 through 21 (predose), Days 22 and 23 (upon morning rising)/ ET and at the Follow-up Visit. Single ECGs will be taken at all visits. Continuous 12-lead Holter ECG monitoring will be conducted from 2 hours predose until 24 hours postdose TAK-071 on Day 1 and from 1 hour predose until 48 hours postdose TAK-071 on Day 21.

For MRD healthy volunteer Cohort 9, a standard 12-lead ECG will be recorded at Screening, Check-in (Day -1), Days 1 and 8 (TAK-071 predose [within 60 minutes prior to dosing] and at 0.5, 1, 2, 4, and 8 hours postdose), and Days 2 to 7 and 9 to 30 upon morning rising/ ET, and at the Follow-up Visit. Single ECGs will be taken at all visits. Continuous 12-lead Holter ECG monitoring will be conducted 2 hours predose until 48 hours postdose on Day 1 and 1 hour predose until 48 hours postdose on Day 28.

For MRD + Donepezil pretreatment healthy volunteer Cohorts 10 to 12, a standard 12-lead ECG will be recorded at Screening, Check-in (Day -22) (donepezil predose [within 60 minutes prior to dosing]), Day -1, Day 1 (TAK-071 predose [within 60 minutes prior to dosing] and at 0.5, 1, 2, 4, and 8 hours postdose), Days 2 to 21 (predose), and Days 22 to 23 (upon morning rising)/ ET and at the Follow-up Visit. Single ECGs will be taken at all visits.

For MRD Japanese healthy volunteer Cohorts 13 to 15, a standard 12-lead ECG will be recorded at Screening, Check-in (Day -1), Days 1 and 8 (TAK-071 predose [within 60 minutes prior to dosing] and at 0.5, 1, 2, 4, and 8 hours postdose). On the remaining days during confinement 12-lead ECG be recorded (upon morning rising)/ ET and at the Follow-up Visit. Single ECGs will be taken at all visits.

For Cohort 16 in subjects with MCI or Mild AD, a standard 12-lead ECG will be recorded at Screening, Check-in (Day -1), Days 1, 21, 41, and 61 (TAK-071 predose [within 60 minutes prior to dosing] and at 0.5, 1, 2, 4, and 8 hours postdose), Days 2, 11, 20 to 22, 40 to 42, 51, and 60 to 62 (upon morning rising)/ ET and at the Follow-up Visit. Single ECGs will be taken at all visits.

For BA/FE Cohort 17, a standard 12-lead ECG will be recorded at Screening, and in each period at Check-in (Day -1), Day 1 (predose [within 45 minutes prior to dosing], and at 0.5, 1, 2, 4, and 8 hours postdose), Days 2 through 5 (upon morning rising), and Day 8 of Period 1 and 2, Study Exit (Day 8 of Period 3)/ ET, and Follow-up Visit Day 12 (± 2), as appropriate.

The investigator (or a qualified observer at the investigational site) will interpret the ECG using 1 of the following categories: within normal limits, abnormal but NCS, or abnormal and CS. The following parameters will be recorded from the subject's ECG trace: heart rate, RR interval, PR interval, QRS interval, and QTcF (QT interval with Fridericia correction method) and QTcB (QT interval with Bazett correction method) interval.

Descriptive statistics (N, mean, SD, median, minimum, and maximum) of the quantitative ECG results will be presented. The changes of ECG results from baseline results will be summarized by the pooled placebo group, each TAK-071 dose level, TAK-071 overall, and overall total within each part (SRD cohorts, MRD cohorts, Cohort 16, and Cohort 17).

All individual ECGs that meet Takeda's predefined criteria for MAV ([Appendix C](#)) will be listed. The number and percentage of subjects with at least one postdose markedly abnormal ECG measurement will be summarized. Subjects who meet the MAV criteria for postdose ECG will be mapped to their respective qualifying ECG result. All postdose MAV ECGs, including both scheduled and unscheduled measurements, will be included in the MAV summaries.

For ECG interpretation data, shift tables will be provided by visit for the number of subjects with each interpretation by the interpretation at baseline.

All other ECG data will be presented in data listings.

Dates and times for the start and stop of continuous 12-lead Holter ECG monitoring will be presented in a data listing. The Holter ECG recordings will be stored, and no data will be extracted for summary and analysis during the conduct of this study.

7.12.5 Other Observations Related to Safety

7.12.5.1 Physical Examination

For SRD Cohorts 1 to 6 and 18 to 22, physical examinations will be performed at Screening, at Check-in (Day -1), Day 5 (Final Visit)/ ET and at the Follow-up Visit.

For MRD healthy volunteer Cohorts 7 and 8, physical examinations will be performed at Screening, at Check-in (Day -1), Day 23 (Final Visit)/ ET and at the Follow-up Visit.

For MRD healthy volunteer Cohort 9, physical examinations will be performed at Screening, at Check-in (Day -1), Day 30 (Final Visit)/ ET and at the Follow-up Visit.

For MRD + Donepezil pretreatment healthy volunteer Cohorts 10 to 12, physical examinations will be performed at Screening, at Check-in (Day -22), Day 23 (Final Visit)/ ET and at the Follow-up Visit.

For MRD Japanese healthy volunteer Cohorts 13 to 15, physical examinations will be performed at Screening, at Check-in (Day -1), Day 30 (Final Visit)/ ET and at the Follow-up Visit.

For Cohort 16 in subjects with MCI or Mild AD, physical examinations will be performed at Screening, at Check-in (Day -1), Day 63 (Final Visit)/ ET and at the Follow-up Visit.

For BA/FE Cohort 17, physical examinations will be performed at Screening, at Check-in (Day -1), and at the Follow-up Visit.

A full physical examination will be conducted at Screening. All other physical examinations will be abbreviated/event driven. A Baseline ophthalmological assessment of the retina (fundoscopy) will be performed at Screening for subjects enrolled in cohorts for CSF sampling.

The physical examination findings will be presented in a data listing. No summary tables will be provided.

The fundoscopy examination results will be presented in a data listing. No summary tables will be provided.

7.12.5.2 Bowel Function

Subjects will be provided with a bowel function diary card during Screening to record their Baseline bowel function using the BSF scale for stool consistency rating.

From Check-in through Final Visit, subjects will use the bowel function diary card to assess the time of each bowel movement during the dosing period (and until 96 hours after the last dose), stool consistency (pictorial BSF score), and completeness of evacuation for an exploratory comparison of the clinical effects of TAK-071.

Stool frequency is defined as the number of episodes of defecation recorded per day in the bowel function card; stool consistency is defined by the 7-point pictorial BSF scale, which ranges from unformed/watery to hard pellets; and sense of complete evacuation is defined by a yes-or-no answer to the question “Did you feel like you completely emptied your bowels?”

For SRD Cohorts 1 to 6 and 18 to 22, at Screening, BSF scale will be obtained at Screening, at Check-in (Day -1), on Days 1 through 5 (Final Visit)/ ET.

For MRD healthy volunteer Cohorts 7 and 8, BSF scale will be obtained at Screening, at Check-in (Day -1), on Days 1 through 23 (Final Visit)/ ET.

For MRD healthy volunteer Cohort 9, BSF scale will be obtained at Screening, at Check-in (Day -1), on Days 1 through 30 (Final Visit)/ ET.

For MRD + Donepezil pretreatment healthy volunteer Cohorts 10 to 12, BSF scale will be obtained at Screening, at Check-in (Day -22), on Days -21 through -1, Days 1 through 23 (Final Visit)/ ET.

For MRD Japanese healthy volunteer Cohorts 13 to 15, BSF scale will be obtained at Screening, at Check-in (Day -1), on Days 1 through 30 (Final Visit)/ ET.

For Cohort 16 in subjects with MCI or Mild AD, BSF scale will be obtained at Screening, at Run-in Period (Day -49 and Day -21), at Check-in (Day -1), on Days 1 through 63 (Final Visit)/ ET.

Descriptive statistics by visit will be presented for the percentage of subjects with BSF scale scores ≥ 6 vs < 6 postbaseline compared with BSF scale scores ≥ 6 vs < 6 at Baseline and for the percentage of subjects with a change from Baseline in BSF scale score of ≥ 2 . Mean change from Baseline in BSF score and stool frequency will also be presented. Summary statistics (N, mean, SD, median, minimum, and maximum) will be generated for continuous variables (eg, time to first stool after dosing and stool frequency), and the number and percentage of subjects within each category will be presented for categorical variables (eg, stool consistency).

The results will be summarized by the pooled placebo group, each TAK-071 dose level, TAK-071 overall, and overall total within each part (SRD cohorts, MRD cohorts, and Cohort 16).

A plot of mean (\pm SD) bowel movement by study day by treatment will be presented.

All BSF data will be presented in a data listing.

7.12.5.3 *Columbia - Suicide Severity Rating Scale (C-SSRS)*

The C-SSRS is an instrument designed to systematically assess and track suicidal behavior and suicidal ideation throughout the trial. The C-SSRS has 4 domains, Suicidal Ideation, Ideation Intensity, Suicidal Behavior and Actual Suicide Attempts.

For SRD Cohorts 1 to 6 and 18 to 22, the C-SSRS will be performed at Screening, at Check-in (Day -1), Day 5 (Final Visit)/ ET. If clinically significant at Final Visit, C-SSRS will also be determined as part of the Follow-up Visit.

For MRD healthy volunteer Cohorts 7 and 8, the C-SSRS will be performed at Screening, at Check-in (Day -1), Day 23 (Final Visit)/ ET. If clinically significant at Final Visit, C-SSRS will also be determined as part of the Follow-up Visit.

For MRD healthy volunteer Cohort 9, the C-SSRS will be performed at Screening, at Check-in (Day -1), Day 30 (Final Visit)/ ET. If clinically significant at Final Visit, C-SSRS will also be determined as part of the Follow-up Visit.

For MRD + Donepezil pretreatment healthy volunteer Cohorts 10 to 12, the C-SSRS will be performed at Screening, at Check-in (Day -22), Day -1, Day 23 (Final Visit)/ ET. If clinically significant at Final Visit, C-SSRS will also be determined as part of the Follow-up Visit.

For MRD Japanese healthy volunteer Cohorts 13 to 15, the C-SSRS will be performed at Screening, at Check-in (Day -1), Day 30 (Final Visit)/ ET. If clinically significant at Final Visit, C-SSRS will also be determined as part of the Follow-up Visit.

For Cohort 16 in subjects with MCI or Mild AD, the C-SSRS will be performed at Screening, at Check-in (Day -1), Day 63 (Final Visit)/ ET. If clinically significant at Final Visit, C-SSRS will also be determined as part of the Follow-up Visit.

For BA/FE Cohort 17, the Screening/Baseline C-SSRS will be administered at Screening and the Since Last Visit C-SSRS will be administered at Day -1 Period 1, at Study Exit (Day 8 Period 3)/ ET, and Follow-up Visit [Period 3 Day 12 (± 2)] (as appropriate, if clinically significant at Study Exit).

C-SSRS data will be presented in data listings. No summary tables will be provided.

7.12.5.4 *Mini Mental State Examination*

The MMSE is an 11-question tool that tests 5 areas of cognitive function: orientation, registration, attention and calculation, recall, and language. The maximum score is 30, with lower scores indicating more cognitive impairment. The MMSE will be administered at Screening to subjects in Cohort 16 only by trained site personnel.

The MMSE results will be presented in data listings. No summary tables will be provided.

7.12.5.5 *Lumbar X-Ray*

Instructions for lumbar x-ray are provided in the Study Manual.

A lumbar x-ray will be performed at Screening in Cohort 3 and Cohort 9 subjects.

Lumbar x-ray data will be presented in data listings. No summary tables will be provided.

7.13 Interim Analysis

[figure not shown]
7.13.1 Interim Analysis of Cohorts 1 to 15 and 17 to 22 Data

Interim analysis of all data (except Cohort 16) will be completed to enable the planning of phase 2 studies, while Cohort 16 enrollment is ongoing. The interim analysis will be initiated once all SRD and MRD cohorts have completed the study.

The main Takeda study team will be unblinded to the data in order to provide interim results to support phase 2 protocol development.

7.13.2 Interim Analysis of PD Data

CC

7.14 Changes in the Statistical Analysis Plan

Only Cohorts 1 to 15 and 17 to 22 will be unblinded after the clinical database freezes. Cohort 16 will remain blinded and be analyzed later.

Appendix A Criteria for Identification of Markedly Abnormal Laboratory Values

Hematology—Criteria for Markedly Abnormal Values

Parameter	Unit	Low Abnormal	High Abnormal
Hemoglobin	Both	$<0.8 \times \text{LLN}$	$>1.2 \times \text{ULN}$
Hematocrit	Both	$<0.8 \times \text{LLN}$	$>1.2 \times \text{ULN}$
RBC count	Both	$<0.8 \times \text{LLN}$	$>1.2 \times \text{ULN}$
WBC count	Both	$<0.5 \times \text{LLN}$	$>1.5 \times \text{ULN}$
Platelet count	Conventional	$<75 \times 10^3/\mu\text{L}$	$>600 \times 10^3/\mu\text{L}$
	SI	$<75 \times 10^9/\text{L}$	$>600 \times 10^9/\text{L}$

LLN=lower limit of normal, RBC=red blood cell, ULN=upper limit of normal, WBC=white blood cell.

Coagulation—Criteria for Markedly Abnormal Values

Parameter	Unit	Low Abnormal	High Abnormal
Prothrombin time/international normalized ratio	Both		$>1.5 \times \text{ULN}$
Activated partial thromboplastin time	Both		$>1.5 \times \text{ULN}$

LLN=lower limit of normal, ULN=upper limit of normal.

Serum Chemistry—Criteria for Markedly Abnormal Values

Parameter	Unit	Low Abnormal	High Abnormal
ALT	Both	--	>3 × ULN
AST	Both	--	>3 × ULN
GGT	Both	--	>3 × ULN
Alkaline phosphatase	Both	--	>3 × ULN
Chloride	Conventional	<75 mEq/L	>126 mEq/L
	SI	<75 mmol/L	>126 mmol/L
Total bilirubin	Conventional	--	>2.0 mg/dL
	SI	--	>34.2 μmol/L
Direct bilirubin	Both	--	>2 ULN
Albumin	Conventional	<2.5 g/dL	--
	SI	<25 g/L	--
Total protein	Both	<0.8 × LLN	>1.2 × ULN
Creatinine	Conventional	--	>2.0 mg/dL
	SI	--	>177 μmol/L
Blood urea nitrogen	Conventional	--	>30 mg/dL
	SI	--	>10.7 mmol/L
Sodium	Conventional	<130 mEq/L	>150 mEq/L
	SI	<130 mmol/L	>150 mmol/L
Potassium	Conventional	<3.0 mEq/L	>6.0 mEq/L
	SI	<3.0 mmol/L	>6.0 mmol/L
Glucose	Conventional	<50 mg/dL	>350 mg/dL
	SI	<2.8 mmol/L	>19.4 mmol/L
Bicarbonate	Conventional	<8.0 mEq/L	
	SI	<8.0 mmol/L	
Creatine kinase	Conventional	--	>5 × ULN
	SI	--	>5 × ULN
Calcium	Conventional	<7.0 mg/dL	>11.5 mg/dL
	SI	<1.75 mmol/L	>2.88 mmol/L

ALT=alanine aminotransferase, AST=aspartate aminotransferase, GGT=γ-glutamyl transferase, LLN=lower limit of normal, ULN=upper limit of normal.

[figure not shown]
Appendix B Criteria for Markedly Abnormal Values for Vital Signs

Parameter	Unit	Lower Criteria	Upper Criteria
Pulse	bpm	<50	>120
Systolic blood pressure	mm Hg	<85	>180
Diastolic blood pressure	mm Hg	<50	>110
Body temperature	°C	<35.6	>37.7
Orthostatic systolic blood pressure	mm Hg	CHG <= -20	
Orthostatic diastolic blood pressure	mm Hg	CHG <= -10	
Orthostatic pulse	bpm		CHG >10

Appendix C Criteria for Markedly Abnormal Values for Electrocardiograms

Parameter	Unit	Lower Criteria	Upper Criteria
Heart Rate	bpm	<50	>120
QT Interval	msec	≤50	≥460
QTcB Interval	msec	≤50	≥500 OR ≥30 change from baseline and ≥450
QTcF Interval	msec	≤50	≥500 OR ≥30 change from baseline and ≥450

ELECTRONIC SIGNATURES

Signed by	Meaning of Signature	Server Date (dd-MMM-yyyy HH:mm 'UTC')
PPD 	Statistical Approval	10-Aug-2017 14:33 UTC
	Clinical VP Approval	10-Aug-2017 16:27 UTC
	Biostatistics Approval	10-Aug-2017 16:37 UTC
	Safety Approval	10-Aug-2017 17:02 UTC
	Clinical Pharmacology Approval	10-Aug-2017 17:15 UTC

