11. The subject has a history of hereditary short QT syndrome.
12. The subject has a Fridericia-corrected QT interval >450 ms or PR interval outside the range 120 to 220 ms, confirmed on repeat testing within a maximum of 30 minutes, at Screening or Check-in.
13. The subject has a positive urine drug result for drugs of abuse (defined as any illicit drug use) at Screening or Check-in.
14. The subject has a history of drug abuse (defined as any illicit drug use) or a history of alcohol abuse within 1 year prior to the Screening Visit; or regularly drinks more than 21 units of alcohol per week in men (or more than 4 units per day) and 14 units in women (or more than 3 units per day); or is unwilling to agree to abstain from alcohol and drugs throughout the study. One unit is equivalent to a half pint of beer, 1 measure of spirits, or 1 glass of wine.
15. There is any finding in the subject's medical history, physical examination, or safety laboratory tests giving reasonable suspicion of a disease that would contraindicate taking TAK-071 (or donepezil for Cohorts 10 to 12, 16, and 20 to 22) or a similar drug in the same class or that might interfere with the conduct of the study.
16. The subject has a risk of suicide or suicidal ideation with intent and plan according to the investigator's clinical judgment (affirmative answer to questions 4 and 5 of the ideation section of the Columbia-Suicide Severity Rating Scale [C-SSRS]) or has made a suicide attempt in the previous 6 months.
17. The subject has taken any excluded medication, supplements, or food products during the time periods listed in the Excluded Medications and Dietary Products table (listed in Section 7.3).
18. The subject has evidence of current cardiovascular, CNS, GI condition, seizure, or any other neurological condition that increases the risk of seizure.
19. Cohort 16 only: Any significant neurologic disease (other than suspected incipient or mild AD), such as Parkinson disease, stroke, transient ischemic attack, multi-infarct dementia, Huntington disease, head trauma with clinically significant cognitive sequelae, or chronic CNS infection, per investigator discretion.
20. Cohorts 9, 10 to 12, and 18 to 22 only: Subjects with a history of eye diseases/ocular pathology (eg, eye injury, cataract surgery, glaucoma).

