5.0 ANALYSIS ENDPOINTS

5.1 Primary Endpoints

The following safety parameters will be analyzed as primary endpoints:

- Percentage of subjects who have at least 1 treatment-emergent adverse event (TEAE).
- Percentage of subjects who meet the Takeda markedly abnormal value (MAV) criteria at least once postdose for the following:
 - Clinical laboratory parameters.
 - Vital sign measurements.
 - ECG parameters.

PK parameters of TAK-071 in plasma following a single dose (Day 1) and at steady-state (after the final dose following multiple dosing) will be analyzed as primary endpoints:

- t_{\max} .
- C_{\max} in plasma.
- Area under the plasma concentration-time curve from time 0 to 24 hours (AUC_{24}).
- Area under the plasma concentration-time curve from time 0 to infinity, calculated using the observed value of the last quantifiable concentration (AUC_{∞}) (single dose only [Day 1]).

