6.0 DETERMINATION OF SAMPLE SIZE

The sample sizes chosen for the SRD and MRD parts are considered to be sufficient for evaluation of safety, tolerability, and PK of each cohort but are not based on statistical power considerations.

A sample size of 12 subjects (4 per sequence) was chosen for the 3-period, 3-sequence, crossover design in Cohort 17. The sample size is considered sufficient to assess the bioavailability of TAK-071 from the tablet relative to the capsule and to assess the effect of food on the bioavailability of TAK-071 from the tablet. This sample size was not based on statistical power considerations.

Enrolled participants who withdraw from the study for reasons other than safety may be replaced to ensure adequate numbers of evaluable subjects. The decision to replace a withdrawn subject will be made at the discretion of Takeda and the investigator.

In addition, in the event of a nonsafety-related critical procedure study interpretation (ie, CSF collection) where a subject is not withdrawn and remains in the study for the completion of all other assessments, that subject may be replaced on a case-by-case basis to ensure evaluability of that particular endpoint (ie, CSF, PK).

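### The QTcF markedly abnormal criterion counts a rise only if the value also reaches 450 ms, so it, and at many heart rates the whole ECG MAV endpoint, can miss rises of 60 ms or more from a low baseline

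*SAP*

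**What the plan says.** SAP section 5.1 makes this a primary safety endpoint: "Percentage of subjects who meet the Takeda markedly abnormal value (MAV) criteria at least once postdose for the following". ECG parameters are one of the three categories listed. SAP section 7.12.4 counts subjects across all ECG rows: "The number and percentage of subjects with at least one postdose markedly abnormal ECG measurement will be summarized".

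The rows are in SAP Appendix C. Heart rate is flagged below 50 or above 120 bpm and uncorrected QT at 460 ms or more. QTcB and QTcF share one upper criterion: "≥500 OR ≥30 change from baseline and ≥450". The table has no row based on change alone. SAP Appendix B does have such rows, for orthostatic blood pressure and pulse.

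Entry is capped from above: "The subject has a Fridericia-corrected QT interval >450 ms or PR interval outside the range 120 to 220 ms" (Protocol section 7.2, item 12). No lower QTcF limit is set.

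Beyond the MAV count, SAP 7.12.4 says "Descriptive statistics (N, mean, SD, median, minimum, and maximum) of the quantitative ECG results will be presented" and "The changes of ECG results from baseline results will be summarized by the pooled placebo group", with the dose levels alongside. It also provides shift tables of the investigator's ECG interpretation. It specifies no table of QTcF rises by size. For Holter, "The Holter ECG recordings will be stored, and no data will be extracted for summary and analysis during the conduct of this study".

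**The concern.** The same rise is counted or not according to where the subject started. A 30 ms rise from 420 ms is an MAV on the QTcF row. A 65 ms rise from 360 ms is not.

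The count is meant to pick out individual subjects in very small groups: 6 on active drug per dose, or 5 in Cohorts 13 to 15. One uncounted subject moves a group from 1/6 = 17% or 1/5 = 20% to 0%. If large rises from low baselines are left out, a zero in the primary ECG table can sit beside a substantial individual QTcF prolongation.

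**Working it through.** The plan gives no power, effect size or QTcF distribution for this point, so there is no stated figure to reproduce. The SAP says that the SRD and MRD sample sizes "are not based on statistical power considerations".

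**Step 1: the QTcF row as a rule.** The criterion can be bracketed as ≥500 or (rise ≥30 and ≥450), or as (≥500 or rise ≥30) and ≥450. The two agree for every integer baseline from 300 to 450 ms and every change from −50 to 199 ms. For an eligible baseline the smallest flagged rise is max(30, 450 − baseline):

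| Baseline (ms) | 350 | 360 | 370 | 380 | 390 | 400 | 410 | 420–450 |
|---|---|---|---|---|---|---|---|---|
| Smallest flagged rise (ms) | 100 | 90 | 80 | 70 | 60 | 50 | 40 | 30 |

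On this row, 380 + 69 = 449 is not flagged and 410 + 40 = 450 is.

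**Step 2: the whole endpoint.** Assume the same heart rate (HR) at baseline and postdose, and RR = 60/HR. Then QT = QTcF × (60/HR)^(1/3) and QTcB = QTcF × (HR/60)^(1/6). For a postdose QTcF of Q:

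- the QT row flags when HR ≤ 60 × (Q/460)^3;
- the QTcB row reaches 450 ms when HR ≥ 60 × (450/Q)^6, and its 30 ms rise condition is also met in the cases below;
- the heart-rate row flags below 50 bpm.

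For Q = 440 the limits are 60 × (440/460)^3 = 52.5 and 60 × (450/440)^6 = 68.7 bpm. The windows in which no row flags are:

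| QTcF change (ms) | Rise (ms) | Unflagged at HR (bpm) |
|---|---|---|
| 380 to 449 | 69 | about 56–61 |
| 380 to 440 | 60 | about 53–69 |
| 370 to 431 | 61 | 50–78 |
| 360 to 425 | 65 | 50–84.5 |
| 350 to 410 | 60 | 50–105 |

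Protocol section 7.2, item 10 admits resting heart rates of 50 to 100 bpm, so the lower windows cover much or all of the eligible range.

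**Step 3: how often.** The documents give no distributions, so these inputs are assumptions: baseline QTcF normal with between-subject SD 15–20 ms, truncated at 450 ms; within-subject SD 6–10 ms; a single-ECG baseline; stable heart rate with mean 60–70 bpm and SD 8. The true rise is 60 ms and is present on one postdose ECG. Percentage of subjects flagged:

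| Mean baseline (ms) | QTcF row alone | Whole endpoint, present | Whole endpoint with ≥60 limb |
|---|---|---|---|
| 390 | about 50 | about 62–75 | about 76–84 |
| 400 | 66–73 | about 76–89 | about 84–93 |
| 410 | 80–89 | about 87–96 | about 91–97 |

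Restricting heart rate to 50–100 bpm lowers the bottom of the whole-endpoint ranges by one or two points (present endpoint 60–75, 75–89 and 86–96).

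**Step 4: false flags from the added limb.** With no drug effect and 9 or 28 postdose ECGs, a change of 60 ms or more occurs in about 0.03% of subjects or fewer at a within-subject SD of 10 ms or less, and in at most about 0.5% at 12 ms.

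**The case against.** The strongest reply is that the endpoint is not the QTcF row. It counts a subject flagged on any ECG row, and QT and QTcB catch many of the cases that QTcF leaves out. This stands. A reader might take 380 to 449 ms as a case that the primary endpoint misses. At a stable heart rate it is missed only between about 56 and 61 bpm. Nor do the QTcF-row detection rates in Step 3 describe the endpoint. But the rescue depends on heart rate and not on the size of the rise, and it weakens as the postdose value falls further below 450 ms.

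Second, large rises are not lost from the report. ECG data are listed, and a large rise would appear in the maximum change if the SAP applies its descriptive statistics to the changes. A change judged clinically significant becomes an adverse event under Protocol section 10.1.3. A reader might also infer that the MAV percentage is the plan's only subject-level ECG count. It is not, because the interpretation shift tables count subjects too, although they do not measure QTcF change. All this narrows the consequence, but none of it puts the rise into the prespecified count.

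Third, requiring both a level and a change is a coherent definition, it is the sponsor's predefined list, and no passage contradicts another. That is fair, and the point is therefore an improvement and not an error in the plan. The 60 ms threshold is likewise a choice that the documents do not supply. It is twice the change already in the rule, and it adds flags only below a 390 ms baseline, because from 390 ms upward a 60 ms rise already reaches 450 ms.

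**Conclusion.** The concern holds for the QTcF criterion, and for the ECG MAV endpoint over a range of heart rates that widens as the baseline falls. Under the Step 3 assumptions, about 25–38% of subjects with a true 60 ms rise on one ECG go uncounted at a mean baseline of 390 ms, 11–24% at 400 ms and 4–13% at 410 ms. The added limb reduces these to about 16–24%, 7–16% and 3–9%. The benefit is material if baselines are low and small if they centre on 410 ms.

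The documents do not support the broader conclusion that large QT prolongation would go unseen in this study. The gap is confined to a prespecified primary count, with no table of rises by size and no Holter extraction in this study to fill it. The percentages depend on assumed QTcF and heart-rate distributions. The rule in Step 1 does not, and the windows in Step 2 assume only a stable heart rate.

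**What to change.** In SAP Appendix C, set the QTcF upper criterion to: ≥500 ms; or a rise of ≥30 ms with a value of ≥450 ms; or a rise of ≥60 ms from baseline. Keep the first two limbs unchanged. In section 7.12.4, report the new limb also as its own count and percentage by dose group and pooled placebo, and keep a separate flag for it so that the MAV percentage under the sponsor's standard list can still be recovered.

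The cost is one clause, one derived flag and one table row, with no new data. The headline ECG MAV percentage may be slightly higher than under the standard list. With no drug effect the added limb contributes about 0.03% of subjects or fewer at a within-subject SD of 10 ms or less, and at most about 0.5% at 12 ms.
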